## **10.3 – Corrective and preventive actions and criteria for disqualification of the Principal Investigator**

In the event of 2 important deviations at the same investigation site, an assessment will be made by the Sponsor and the site principal Investigator may be disqualified. In that case, the inclusions will be stopped at that site.

## **XI – DEVICE ACCOUNTABILITY**

 <small>ARTIFICIAL INTELLIGENCE SERVING HUMANITY BETTER</small>	CLIPL-01-002-E	CONFIDENTIAL
	CLINICAL INVESTIGATION PLAN	F 09 XX 01 Rev.A

The Principal Investigator of each site shall maintain adequate records of the receipt and disposition of all devices per local institutional procedures and regulations.

## **XII – STATEMENTS OF COMPLIANCE**

### **12.1 – Ethical and regulatory considerations**

The study will be conducted in accordance with the ethical principles mentioned in the Declaration of Helsinki (cf. Appendix 18.1), Good Clinical Practice, the ISO 14155 Standard and applicable laws and country regulations where the study will be performed.

This study would not start until approvals or favorable opinions have been received from applicable Ethics Committees or IRBs and Regulatory Authorities.

Each amendment to this Clinical Investigation Plan must be approved beforehand by the applicable Ethics Committees or IRBs and Regulatory Authorities for the full duration of the Study.

Any requirements imposed by the applicable Ethics Committees, IRBs and/or Regulatory Authorities shall be respected and applied throughout the Study period.

### **12.2 – Insurance**

Provided that this protocol is respected, the civil liability of Volta Medical and all its agents is covered by a contract subscribed by Volta Medical with HDI GLOBAL SE (contracts nos. 0100534514058-200083 for France, 390-76236600-30016 for Belgium, 76237332-03032 for Germany and V-071-369-378-0 for The Netherlands). A copy of the insurance certificates can be found in Appendix 18.2.

## **XIII – INFORMED CONSENT PROCESS**

To participate in the study, the subject must sign and date the Informed Consent Form after having been informed about the nature and purpose of the Study, participation and termination conditions, risks, and benefits, before initiation of any study-related procedures. Patient Information and Patient Informed Consent Form are provided in Appendix 18.4.

A copy of the signed Informed Consent Form must be provided to the participating patient.

The patient information and Informed Consent Form will be available in certified translation in all official languages of the countries participating in the Study.

Signed Informed Consent Forms must remain in the patients' study files and be available for verification by the Sponsor or representative at any time.

## **XIV – ADVERSE EVENTS, ADVERSE DEVICE EFFECTS AND DEVICE DEFICIENCIES**

### **14.1 – Definitions (according to ISO 14155:2020)**

#### **Adverse Event (AE)**

 <small>ARTIFICIAL INTELLIGENCE SERVING HUMANITY</small>	CLIPL-01-002-E	CONFIDENTIAL
	CLINICAL INVESTIGATION PLAN	F 09 XX 01 Rev.A
		Page 40/47

Untoward medical occurrence, unintended disease or injury, or untoward clinical signs (including abnormal laboratory findings) in subjects, users or other persons, whether or not related to the investigational medical device and whether anticipated or unanticipated.

NOTE 1: This definition includes events related to the investigational medical device or the comparator.

NOTE 2: This definition includes events related to the procedures involved.

NOTE 3: For users or other persons, this definition is restricted to events related to the use of investigational medical devices or comparators.

#### **Adverse Device Effect (ADE)**

Adverse event related to the use of an investigational medical device.

NOTE 1: This definition includes adverse events resulting from insufficient or inadequate instructions for use, deployment, implantation, installation, or operation, or any malfunction of the investigational medical device.

NOTE 2: This definition includes any event resulting from use error or from intentional misuse of the investigational medical device.

NOTE 3: This includes 'comparator' if the comparator is a medical device.

#### **Serious Adverse Event (SAE)**

Adverse event that led to any of the following:

- a) death,
- b) serious deterioration in the health of the subject, users, or other persons as defined by one or more of the following:
  - a life-threatening illness or injury, or
  - a permanent impairment of a body structure or a body function including chronic diseases, or
  - in-patient or prolonged hospitalization, or
  - medical or surgical intervention to prevent life-threatening illness or injury, or permanent impairment to a body structure or a body function.
- c) foetal distress, foetal death, a congenital abnormality, or birth defect including physical or mental impairment.

NOTE 1: Planned hospitalization for a pre-existing condition, or a procedure required by the CIP, without serious deterioration in health, is not considered a serious adverse event.

#### **Serious Adverse Device Effect (SADE)**

Adverse device effect that has resulted in any of the consequences characteristic of a serious adverse event.

#### **Unanticipated Serious Adverse Device Effect (USADE)**

Serious adverse device effect which by its nature, incidence, severity or outcome has not been identified in the current risk assessment.

NOTE 1: Anticipated serious adverse device effect (ASADE) is an effect which by its nature, incidence, severity or outcome has been identified in the risk assessment.

#### **Device deficiency**

Inadequacy of a medical device with respect to its identity, quality, durability, reliability, usability, safety or performance.

NOTE 1: Device deficiencies include malfunctions, use errors, and inadequacy in the information supplied by the manufacturer including labelling.

NOTE 2: This definition includes device deficiencies related to the investigational medical device or the comparator.

#### **Device malfunction**

 <small>ARTIFICIAL INTELLIGENCE SERVING HUMANITY BETTER</small>	CLIPL-01-002-E	CONFIDENTIAL
	CLINICAL INVESTIGATION PLAN	F 09 XX 01 Rev.A

Failure of an investigational medical device to perform in accordance with its intended purpose when used in accordance with the instructions for use or CIP, or IB.

#### **Use error**

User action or lack of user action while using the medical device that leads to a different result than that intended by the manufacturer or expected by the user.

NOTE 1: Use error includes the inability of the user to complete a task.

NOTE 2: Use errors can result from a mismatch between the characteristics of the user, user interface, task or use environment.

NOTE 3: Users might be aware or unaware that a use error has occurred.

NOTE 4: An unexpected physiological response of the patient is not by itself considered a use error.

NOTE 5: A malfunction of a medical device that causes an unexpected result is not considered a use error.

#### **14.2 – Adverse event evaluation and reporting**

Conditions or diseases which are pre-existing and chronic should not be recorded as adverse events. Changes in a chronic condition or disease that are consistent with natural disease progression are not considered adverse events. Pre-existing conditions or diseases should be documented as part of the patient's medical history.

Elective or pre-planned treatments for AF (e.g. scheduled re-ablation or cardioversion) which are part of the patient's scheduled treatment plan should not be considered adverse events. However, any events related to a procedure (including re-do procedure) or the patient's underlying AF which are not expected or indicate a worsening of condition should be reported as adverse events.

The adverse event should be recorded in standard medical terminology rather than the patient's own words when possible.

The investigator will assess each adverse event for its relationship to the study device, and whether it was anticipated in the protocol. The determination of the relationship between the adverse event and the device or procedure is made according to the following definitions:

- Definitely related (causal relationship): the adverse event was directly and clearly related to the device or procedure
- Probably related
- Possibly related
- Not related
- Unknown

Adverse events that are serious and/or unanticipated will be reviewed immediately by Labcorp and Volta employees or representatives and will also be reviewed during DSMB meetings.

All adverse events are listed in the eCRF.

All serious adverse events (SAEs, SADEs, USADEs) should be emailed to [[contact]](mailto:[contact]) within 24 hours from the become aware date. The following information should be collected:

- Nature of adverse event
- Date of onset of adverse event
- Date of resolution of adverse event, if applicable
- Statement as to why it is considered serious
- Statement as to why it is considered unanticipated, if applicable
- Statement as to the degree to which it is considered device related, and why

- Results of any diagnostic tests performed
- Description of any intervention performed, or treatment administered

It is the responsibility of each investigator to report all SAEs/SADEs/USADEs to the Ethics Committee or IRB, according to national regulations and EC/IRB requirements.

Volta Medical will assure that Labcorp employee or representative will report all serious adverse events to the corresponding Competent Authorities in accordance with all applicable national regulations.

#### **14.3 – Anticipated adverse events**

Table 10 provides the list of all anticipated adverse events related to AF ablation.

*Table 10: Anticipated Adverse Events*

Description	Description
Abnormal ECG	Pericardial effusion
Local normal discomfort due to insertion/removal of vascular sheaths	Cardiac tamponade due to perforation
Hemorrhage and/or hematoma at sheath insertion	Nerve injury
Extremity weakness, swelling and/or pain	Air embolism
Complete AV block	Allergic reaction
Nausea/vomiting	Endocarditis
Shortness of breath/dyspnea	Esophageal-atria fistula
Feeling of chest pain, skipped beats, and/or rapid heart rate	Hemothorax
Damage to skin from prolonged exposure to x-rays	Pericarditis
New arrhythmias	Pseudoaneurysm
Ventricular arrhythmia requiring defibrillation	Pulmonary vein dissection/stenosis
Arterial injury requiring intervention	Respiratory failure
Thromboembolism	Stroke/TIA
Local/systemic infection	Valvular damage
Pneumothorax	Pleural effusion
AV fistula	Pulmonary edema
Thrombophlebitis	Anemia requiring transfusion
Pulmonary embolism	Vasovagal reaction
Myocardial infarction	Hypotension
Heart failure	Death (must be reported as SAE)

#### **14.4 – Data Safety Monitoring Board (DSMB)**

A board of independent experts will review the study data to determine the progress of the study from a safety point of view and will independently make recommendations to the Steering Committee to continue, to modify or to terminate the clinical study.

The DSMB will consider relevant background knowledge about the disease, therapies, or patient population as well as study-specific data, in order to monitor the conduct of the study to evaluate the safety of the subjects involved in the trial, to evaluate the occurrence of early unanticipated adverse effects.

 <small>ARTIFICIAL INTELLIGENCE SERVING HUMANITY BETTER</small>	CLIPL-01-002-E	CONFIDENTIAL
	CLINICAL INVESTIGATION PLAN	F 09 XX 01 Rev.A
		Page 43/47

In particular, the board will review all the Adverse Events in order to ascertain evidence of a safety risk in continuing the study.

The DSMB is made of three independent EP experts (cf. Appendix 18.8).

## **XV – SUSPENSION OR PREMATURE TERMINATION OF THE CLINICAL INVESTIGATION**

### **15.1 – Criteria and provisions**

Premature, definitive, or temporary termination of all or part of the study may be decided by Ethics Committees, IRBs, Competent Authorities or the Sponsor.

If an adverse effect due to the implementation of the protocol is observed, the study may be suspended at any time by the Sponsor. If no satisfactory solution can be found to the problem, the study may be stopped completely; if a satisfactory solution is found, the study may be resumed.

Premature termination of the study may occur motivated by a general decision (Ethics Committees, IRBs, regulatory Competent Authorities, Data Safety Monitoring Board) for safety reasons related to the use of the device or study procedures.

A site may be terminated for the following reasons: failure to comply with the conditions of the study protocol and/or failure to accurately complete case report forms.

### **15.2 – Patient follow-up requirements**

At the end of the study, medical management of patients will consist of standard post-ablation follow-up, regardless of whether the study has ended normally or prematurely.

## **XVI – STUDY REPORT AND PUBLICATION POLICY**

After conclusion of the investigation, a comprehensive clinical and statistical report shall be written by Volta Medical in consultation with the Coordinating Investigator.

The first publication will be a full publication of all data from all sites. Any publications of the results, either in part or in total (abstracts in journals or newspapers, oral presentations, etc.) by investigators or their representatives will require pre-submission review by Volta Medical. Volta Medical is entitled to delay publication in order to obtain patent protection. For more details regarding publications, refer to the publication Agreement.

## **XVIII – APPENDICES**

- 18.1 – Declaration of Helsinki**
- 18.2 – Insurance Certificate**
- 18.3 – CE Certificates**
- 18.4 – Patient Information and Patient Informed Consent**
- 18.5 – Investigator Agreement**
- 18.6 – IFU or Investigator's Brochure**
- 18.7 – List of Investigators**
- 18.8 – Study Boards**

The Tailored-AF trial

**Tailored** vs Anatomical Ablation Strategy for Persistent Atrial **F**ibrillation

NCT Number: NCT04702451

Protocol ID: CLIPL-01-002

Document type: Statistical Analysis Plan

Document version: 1.4

Document date: 19/FEB/2024

Volta Medical

Tailored vs. Anatomical Ablation Strategy for Persistent AF CLIPL-01-002-E

Statistical Analysis Plan

Version: 1.4

Volta Medical [name]

CONFIDENTIAL DO NOT COPY

This document contains information that is confidential and proprietary. The contents of this document may not be copied without written permission from Volta Medical.

Version: 1.4

TABLE OF CONTENTS

1	PRO	PROTOCOL SUMMARY 3			
2	ABBREVIATIONS5				
3	INTRODUCTION				
4	ENDPOINT ANALYSES				
	4.1	ANALYSIS SETS	6		
	4.2	PRIMARY ENDPOINT	7		
	4.3	SECONDARY ENDPOINTS			
	4.4	EXPLORATORY ENDPOINTS	10		
	4.5	SAFETY ENDPOINTS	11		
5		ESSING THE PRIMARY OUTCOME			
6	GENERAL STATISTICAL CONSIDERATIONS				
	6.1	INTERIM ANALYSIS	14		
	6.2	BLANKING PERIODS	15		
	6.3	MISSING DATA MANAGEMENT			
	6.4	POOLING DATA ACROSS CENTERS	16		
	6.5	RANDOMIZATION	16		
	6.6	TREATMENT MASKING			
	6.7	STUDY STOPPING RULES			
	6.8	MEASURES TAKEN TO MINIMIZE BIAS	17		
	6.9	CORRECTION FOR MULTIPLE-TESTING			
7		NGES FROM PROTOCOL			
8	REF	ERENCES	18		

1 Protocol Summary

Drimon, Objective	To demonstrate that a tailored oblation strategy towarding areas
Primary Objective	To demonstrate that a tailored ablation strategy targeting areas
	exhibiting spatio-temporal dispersion in association with PVI, is superior
	to an anatomical probabilistic ablation strategy targeting PVI alone for
	the treatment of persistent AF.
Study	Tailored ablation with VX1
Device/Procedure	
Control	Anatomical Ablation
Device/Procedure	
Study Design	Interventional, prospective, randomized, controlled, two-arm,
	multicenter clinical investigation
Primary Endpoint(s)	Freedom from documented AF, with or without AADs, 12 months after
	a single AF ablation procedure. Where freedom from documented AF is
	defined as no documented episodes of AF>30 seconds with
	conventional non-invasive monitoring between 3 and 12 months after
	index procedure. Freedom from AF is analyzed as a time-to-event
	comparison between survival distributions of the treatment and control
	arms.
Secondary	Freedom from documented AF/AT, after one or two procedures, with
Endpoint(s)	or without AADs, at 12 months
Ziiapoiiii(o)	2. Freedom from documented AF/AT, after one procedure, with or
	without AADs, at 12 months
	·
	· · · · · · · · · · · · · · · · · · ·
	serious treatment-related adverse event at 12 months after index
	procedure.

Exploratory Endpoints

- 1. Freedom from documented AF, after one or two procedures, with or without AADs, at 12 months
- 2. Freedom from documented AF or AF/AT, after one procedure, or one procedure or more, without AADs, at 12 months
- 3. Freedom from documented AF or AF/AT, after one procedure, or one procedure or more, without AADs or with previously failed AAD at the same dose, at 12 months
- 4. Freedom from documented AF or AF/AT, after one procedure, or one procedure or more, with or without AADs, at 12 months, without the use of TTM
- 5. Freedom from documented symptomatic AF or AF/AT, after one procedure, or one procedure or more, with or without AADs, at 12 months
- Freedom from AF or AF/AT, with or without AADs, 12 months after one procedure, or one procedure or more, for subjects with persistent AF <1 year
- 7. Quality of life measurements (SF-36 and AFEQT) at baseline, 3, 6 and 12 months post-index procedure
- 8. Incidence of peri-procedural complications including stroke, PV stenosis, cardiac perforation, esophageal injury, and death
- 9. Acute AF termination rate by ablation
- 10. Rate of conversion to sinus rhythm by ablation
- 11. Ablation procedure duration
- 12. Fluoroscopy time and dose
- 13. Mapping time
- 14. Radiofrequency (RF) time to terminate AF
- 15. Total RF time
- 16. Total delivered energy (mean power x RF duration)
- 17. Total delivered energy (mean power x RF duration) / biatrial surface
- 18. Ablation surface area to terminate AF
- 19. Total ablation surface area
- 20. Blinded baseline Voltage maps before ablation
- 21. TTM compliance (% of transmissions expected vs received at each week post index procedure)
- 22. Assessment of blind maintenance per group

Follow-Up Schedule

Follow-up assessments at 3, 6, and 12 months post index procedure. Holter and 12-lead ECGs will be performed at 3, 6, and 12 months. Portable trans telephonic event monitors will be recorded weekly for approximately 52 weeks.

2 Abbreviations

AAD	Antiarrhythmic Drug
ADE	Adverse Device Effect
AE	Adverse Event
AF	Atrial Fibrillation
AFEQT	AF Effect on Quality-of-Life Questionnaire
AT	Atrial Tachycardia
СР	Conditional Power
ECG	Electrocardiogram
HR	Hazard Ratio
mITT	Modified Intention-To-Treat
PP	Per-Protocol
PV	Pulmonary Vein
PVI	Pulmonary Vein Isolation
QoL	Quality-of-Life
RF	Radio Frequency
SADE	Serious Adverse Device Effect
SAE	Serious Adverse Event
SAP	Statistical Analysis Plan
SF-36	The Short Form (36) Health Survey
ТТМ	Trans Telephonic Monitoring

3 Introduction

This statistical analysis plan (SAP) describes the planned analyses for data collected under the Clinical Trial Protocol CLIPL-01-002 "Tailored vs. Anatomical Ablation Strategy for Persistent AF", last revised 06 July 2022 (Revision E). Specified analyses may be used for scientific presentations and/or manuscripts, and regulatory submissions. The primary analysis will be based on the data through 12 months post-index procedure.

If there are any discrepancies between this SAP and the study protocol, the SAP shall prevail.

4 Endpoint Analyses

4.1 ANALYSIS SETS

The analysis sets making up this study will include the following:

4.1.1 The Safety Population

The Safety population will include all randomized Subjects who underwent their first ablation procedure.

4.1.2 The Modified Intent-to-Treat Population (mITT)

The modified Intention-To-Treat (mITT) set will include all randomized subjects except for:

- Subjects who are deemed ineligible after randomization or who do not have any AF ablation, and
- Subjects lost to follow-up during the 3-month blanking period.

Subjects in the Tailored group for whom AF cannot be induced and who undergo conventional ablation will be included in the mITT analysis.

Subjects who complete at least their 3-month follow-up visit but who are lost to follow-up before the 12-month follow-up visit will be included in the mITT analysis.

Subjects who undergo a 3rd ablation procedure will be included in the analyses but the data will be censored at the time of the 3rd procedure for multiple procedure endpoints.

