### 5.3.8 – Blanking periods

After the index procedure, a 6-week absolute blanking period will be applied, during which a repeat procedure is not allowed, only cardioversions are allowed if necessary.

After this absolute blanking period and before the end of the standard 3-month blanking period, a repeat procedure is discouraged but not prohibited. The decision to perform a repeat procedure before the end of the 3-month blanking period is left to the operator's discretion. If a repeat procedure is performed during the 3-month blanking period, the recurrence and the repeat procedure are counted as occurring at 3 months.

After a repeat procedure, a 2-week blanking period will be applied, during which AF/AT recurrences will not be counted. Any re-repeat procedures will be performed outside the study according to the operator's preferred approach and will result in the data being censored at the time of the re-repeat procedure. The patient will however stay in the study for safety purposes.

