### 5.3.9 – Visit schedule

Study visits that do not occur within time windows in Table 8 will be considered protocol deviations.

Table 8: Time windows for study visits

Visit	Screening, enrollment, and randomization	Index procedure	3-month follow-up	Redo procedure (if required)	6-month follow-up	12-month follow-up
Timing	Prior to index procedure	0 – 90 days after enrollment	2M + 1 day to 3M after index procedure	3M to 9M after index procedure	6M ± 30 days after index procedure	12M ± 30 days after index procedure

5.3.10 – Summary of required clinical assessment and data collection

Table 9 summarizes study visits and required assessments and data collection.

*Table 9: Schedule of events*

Event	Screening	Enrollment	Index procedure	3-month follow-up visit	Redo procedure (if required)	6-month follow-up visit	12-month follow-up visit	Unscheduled follow-up visit
Inclusion and exclusion criteria assessment	X							
Informed consent	X							
Demographics, medical history, cardiac diagnosis		X						
Documentation of AF (ECG, physician's letter)		X						
12-lead ECG		X		X		X	X	X
Physical exam		X		X		X	X	X
Concomitant cardiac medications		X	X	X	X	X	X	X
AF assessment (AF presence and/or AF recurrence since last follow-up)		X	X	X	X	X	X	X
QoL questionnaire		X		X		X	X	
24h ambulatory continuous ECG (Holter)				X		X	X	
Adverse Events review		X	X	X	X	X	X	X
AF interventional procedure			X		X			

 <small>ARTIFICIAL INTELLIGENCE SERVING HEART DISEASE</small>	CLIPL-01-002-E	CONFIDENTIAL
	CLINICAL INVESTIGATION PLAN	F 09 XX 01 Rev.A

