## **VI – STATISTICAL CONSIDERATIONS**

### **6.1 – Design, statistical methodology and analytical procedures**

Standard summary statistics will be calculated for all study variables (demographics and outcomes) by study group and for all patients. For continuous variables, statistics will include means, standard deviation and 95% confidence intervals for means when assumptions of normal distribution are not violated. Median and quartiles may also be presented. Categorical variables will be summarized using frequency distributions.

The analysis for the primary endpoint will be a modified Intention-To-Treat (mITT) analysis, allowing exclusion of some randomized subjects in a justified way:

- Patients that are deemed ineligible after randomization or that do not have any AF ablation will be excluded
- Patients in the Tailored group for whom AF cannot be induced and who undergo conventional ablation will be included in this analysis
- Patients lost to follow-up (death, disability, relocation, or drop-out) during the 3-month blanking period will be excluded
- Patients who complete at least their 3-month follow-up but who are lost to follow-up (death, disability, relocation, or drop-out) before the 12-month follow-up will be included in the analysis and the data will be censored
- Patients who undergo a 3rd ablation procedure (re-repeat procedure) will be included in the analysis but the data will be censored at the time of the 3rd procedure.

A per-protocol (PP) population will also be evaluated and will serve as supportive analyses to the mITT analysis. In the PP analysis, the population will be analyzed according to the treatment actually received at the start of the study, and will consist of patients that met all the inclusion criteria, none of the exclusion criteria, were successfully treated, had no important protocol deviations and attended all the scheduled follow-up visits.

 <small>ARTIFICIAL INTELLIGENCE SERVING HEART DISEASE</small>	CLIPL-01-002-E	CONFIDENTIAL
	CLINICAL INVESTIGATION PLAN	F 09 XX 01 Rev.A Page 33/47

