4.5.1 Other Adverse Events

All adverse events will be summarized through 12 months. The proportions of subjects with events will be reported. No imputation for missing data is planned.

Tabular summaries by treatment group of all adverse events, adverse device effects, serious adverse events, and serious adverse device effects will be presented.

An adverse event (AE) is defined as any untoward medical occurrence, unintended disease or injury or untoward clinical signs (including an abnormal laboratory finding) in subjects,

users or other persons, whether or not related to the investigational medical device. An Adverse Device Effect (ADE) is defined as an adverse event related to the use of an investigational medical device. A serious adverse event (SAE) is an adverse event that:

- a) led to a death
- b) led to a serious deterioration in the health of the subject, that either resulted in: a life-threatening illness or injury, or a permanent impairment of a body structure or a body function, or in-patient or prolonged hospitalization, or -medical or surgical intervention to prevent life threatening illness or injury or permanent impairment to a body structure or a body function.
- c) led to fetal distress, fetal death or a congenital abnormality or birth defect. A serious adverse device effect (SADE) is an adverse device effect that has resulted in any of the consequences characteristic of a serious adverse event.

The investigator will assess each adverse event for its relationship to the study device, and whether it was anticipated in the protocol. The determination of the relationship between the adverse event and the device is made according to the following definitions:

- Definitely related (causal relationship)
- Probably related
- Possibly related
- Not related
- Unknown.

Acute peri-procedural complications (related to the study procedure and occurring within one week of the ablation procedure), will be specifically analyzed as part of the exploratory endpoints.

5 Assessing the Primary Outcome

Freedom from documented AF between 3 and 12 months following the index ablation procedure will be defined as no documented episodes of AF > 30 seconds with conventional non-invasive monitoring.

The following scenarios result in primary endpoint failure:

- 1) A repeat procedure where AF is confirmed during the procedure (Patient is in spontaneous AF at the beginning of the procedure)

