6.2 BLANKING PERIODS

After the index procedure, a 3-month blanking period + tolerance of 1 week (98 days) will be applied for all efficacy endpoints, during which recurrences of AF/AT (excluding repeat procedure) will not be counted.

If a repeat procedure is performed during the 3-month blanking period (and patient is in spontaneous AF), the recurrence and the repeat procedure will be counted as occurring at 3 months.

If a repeat procedure is performed after the end of the 9th month, the procedure will not be considered for multiple procedures endpoints.

After a repeat procedure, a 2-week blanking period (14 days) will be applied, during which AF/AT recurrences will not be counted. Any re-repeat procedures (repeat procedure #2) will result in the data being censored at the time of the re-repeat procedure.

Note: for the purpose of counting months to establish blanking period boundaries in the study, one month will be considered equal to 30.4 days.

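### The mITT rule for loss during blanking makes no exception for a subject whose early repeat procedure already counts as a primary failure

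*SAP*

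**What the plan says.** **Exclusion.** SAP 4.1.2 leaves out of the mITT set "Subjects lost to follow-up during the 3-month blanking period", with no exception. Protocol 6.1 has the same rule with a broader definition of loss: "Patients lost to follow-up (death, disability, relocation, or drop-out) during the 3-month blanking period will be excluded".

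**Inclusion.** Later in SAP 4.1.2: "Subjects who complete at least their 3-month follow-up visit but who are lost to follow-up before the 12-month follow-up visit will be included". Protocol Table 8 sets the window for that visit at "2M + 1 day to 3M after index procedure".

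**Events during blanking.** SAP 6.2 sets a blanking period of 98 days, "during which recurrences of AF/AT (excluding repeat procedure) will not be counted". If a repeat procedure takes place in blanking and the patient is in spontaneous AF, "the recurrence and the repeat procedure will be counted as occurring at 3 months". SAP section 5 lists among the primary failures "A repeat procedure where AF is confirmed during the procedure", which it limits to spontaneous AF at the start of that procedure.

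**When an early repeat procedure can occur.** Protocol 5.3.8 says "a 6-week absolute blanking period will be applied, during which a repeat procedure is not allowed". From then to month 3 it advises against a repeat procedure but leaves the decision to the operator.

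**Analyses.** The primary analysis is run in mITT (SAP 4.2.3). The only named sensitivity analysis is per-protocol (SAP 4.2.4). SAP 6.3 promises further analyses of missing data without describing them.

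**The concern.** Two rules apply to the same subject and give opposite results. SAP 6.2 and section 5 make an early repeat procedure in AF a primary failure. SAP 4.1.2 removes that subject if loss follows before blanking ends. Nothing says which rule prevails.

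This would be an exclusion after randomisation that discards an outcome already observed. It also does little else to the test. A subject who is event-free and lost before month 3 is in no risk set at any countable event time, so removing or censoring that subject leaves the log-rank statistic unchanged. The subjects whose removal can change it are essentially those with an early-redo event.

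If the text stays as it is, whether a known failure counts may have to be settled case by case with data in hand.

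**Working it through.** **1. The plan's own figure.** Inputs from SAP 4.2.2: 62% and 77% AF-free, one-sided 0.025, 80% power.
- HR = ln(0.77)/ln(0.62) = 0.547, as stated.
- Log-rank power by the Lakatos method (exponential curves, fixed follow-up) at N = 292 is 80.02%, with about 89 events. The stated 292 reproduces.
- 292/(1 − 0.22) = 374.4, against 374 stated.

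This point disputes none of these numbers, and the fix leaves them unchanged.

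**2. The collision on a timeline** (one month = 30.4 days, SAP 6.2).
- A repeat procedure is possible from week 6 = day 42.
- Month 3 = 3 × 30.4 = day 91.2. Blanking with its one-week tolerance ends on day 98.
- Example: repeat procedure in spontaneous AF at week 8 (day 56), loss at week 11 (day 77). SAP 6.2 gives a primary event at about day 91. SAP 4.1.2 gives no place in the mITT set.

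**3. The overlap.** The 3-month visit opens at 2 × 30.4 + 1 = 61.8, about day 62. A subject seen on day 65 and lost on day 80 meets both the exclusion and the inclusion sentence. This does not require an early repeat procedure.

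**4. How many subjects.** The documents give no rate. *Assumption:* 1–10% of 374 have a repeat procedure in AF between week 6 and month 3, and 1–10% of those are lost before blanking ends.
- Low: 374 × 0.01 × 0.01 = 0.04
- Middle: 374 × 0.05 × 0.05 = 0.94. The Poisson chance of none is e^(−0.94) = 0.39, and of none or one 0.39 × (1 + 0.94) = 0.76.
- High: 374 × 0.10 × 0.10 = 3.7

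**5. Shift in the hazard ratio per deleted failure.** Planning rates, 146 per arm: expected failures are 146 × 0.23 = 33.58 (Tailored) and 146 × 0.38 = 55.48 (Anatomical). With k failures deleted, the arm's AF-free share becomes 1 − (events − k)/(146 − k), and HR is the ratio of the logs. For k = 1 in Tailored: 1 − 32.58/145 = 0.7753, and ln(0.7753)/ln(0.62) = 0.532.

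| k deleted | Tailored only | Anatomical only | k in each arm |
|---|---|---|---|
| 0 | 0.547 | 0.547 | 0.547 |
| 1 | 0.532 | 0.555 | 0.540 |
| 3 | 0.503 | 0.572 | 0.526 |

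**6. One-sided error with no true effect.** Simulated log-rank test, 146 per arm, 62% AF-free in both arms.
- The 1, 2 or 3 earliest failures always deleted from Tailored and none from Anatomical: 3.1%, 3.9%, 4.9%.
- Deleted from Anatomical only: about 2.0%, 1.6%, 1.4%.
- The rule applied to both arms at the highest assumed rates (10% and 10%): 2.5%.

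**The case against.** **What loss means.** The example of a death or withdrawal relies on the protocol's list (6.1, repeated in 6.7). The SAP omits that list, describes loss in 6.3 as failure to locate the subject after three attempts, and prevails over the protocol where they differ (SAP section 3). Protocol 5.2.3 also lists death, withdrawal and loss separately. This stands as an ambiguity. The narrow reading shrinks the group but does not empty it, since a subject who cannot be located after an early repeat procedure is still excluded.

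**Inflated type I error.** A reader might infer that the rule raises the one-sided error to 3–5%. The documents do not support that. Those figures need every affected subject to be in the Tailored arm, and nothing in the plan points to this. The same rule governs both arms, and non-differential loss leaves the test at its nominal size.

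**Bias towards the device.** This might also be inferred, but losses in the Anatomical arm work against the device.

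**Rarity.** Repeat procedures are barred for six weeks and advised against until month 3. SAP 6.9 expects 22–33% of patients to have a second procedure. A 10% early rate would put 10/33 = 30% to 10/22 = 45% of them into about seven weeks, so the upper counts are strained. No affected subject is shown to exist.

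**The overlap.** The inclusion sentence can be read as the more specific rule, and for event-free subjects the choice hardly affects the test. Both points are fair; together they make the overlap small but do not resolve it.

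**Other analyses.** The missing-data analyses in SAP 6.3 might retain these subjects, but they are not specified. The per-protocol set is narrower than mITT.

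**Conclusion.** The rule is wrong as written, and the severity is minor. Applied literally, SAP 4.1.2 drops a subject whom SAP 6.2 and section 5 have already counted as a primary failure, and its inclusion and exclusion sentences overlap from about day 62 to the end of blanking.

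The likely size is none or one patient, and about four at the top of the assumed rates, which do not come from the documents. On the planning figures, each deleted failure moves the hazard ratio by about 0.015 downward if it is in the Tailored arm (0.547 to 0.532), or about 0.008 upward if in the Anatomical arm (0.547 to 0.555). The direction is not fixed, and with equal action in both arms the one-sided error stays near 2.5%. The point does not show that the primary result would be biased. It shows that a known event should not depend on an unresolved rule.

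**What to change.** Reword the second bullet of SAP 4.1.2, for example: *Subjects lost to follow-up before the end of the blanking period who have no primary-endpoint event; a subject whose repeat procedure is counted as a failure at 3 months stays in the mITT set as an event at 3 months, regardless of later loss.*

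Tie both this bullet and the inclusion sentence to one stated day for the end of blanking, in place of attendance at the 3-month visit. The SAP's own text gives 98 days. State also whether loss includes death and withdrawal, so that the SAP and Protocol 6.1 agree.

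Deleting the bullet and censoring at loss is not enough on its own. In the example, censoring at day 77 would precede the assigned event at about day 91, and the failure would still go uncounted.

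Cost: a short SAP edit, no new data, and no change to 292 or 374. The reported AF-free rate may be slightly less favourable.
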